### B1. PURPOSE OF PROTOCOL

The primary objectives of this study are:

- To evaluate the clinical response of patients with diarrhea to crofelemer relative to placebo.
- To evaluate the overall safety and tolerability of crofelemer in the treatment of diarrhea.

The secondary objective of this study is assess whether improvement in bowel function with crofelemer is more effective in subjects without evidence of bile acid malabsorption (i.e., elevated C4 level).

### B2. SIGNIFICANCE AND BACKGROUND FOR THE STUDY

Irritable bowel syndrome (IBS) is a gastrointestinal condition defined by abdominal pain and altered bowel habits in the absence of another disease that can account for these symptoms (1). IBS is the most commonly diagnosed gastrointestinal condition and has a population prevalence of up to 12% in North America (1–3). IBS is more prevalent in women than in men (4). Depending on diagnostic criteria and study methodology, anywhere from 0.8–50% of IBS patients in the United States suffer from the diarrhea-predominant IBS subtype (IBS-D), in which altered bowel habits are most frequently diarrhea (5). Patients with IBS-D and IBS in general report significantly reduced quality of life, higher indirect costs, and greater impairments in daily and work activities (6–10). Limited medication options are available for treatment of diarrhea symptoms associated with IBS-D.

Crofelemer is a potent antisecretory agent and has promising therapeutic properties for functional diarrhea patients. Crofelemer is an active compound extracted from the latex of the Western South American plant *Croton lechleri*. The latex has been used for medicinal purposes for centuries by indigenous peoples, with its active properties attributable to the crofelemer compound (11). Crofelemer has an inhibitory effect on cAMP-mediated secretion of chloride ions in T84 and Caco-2 epithelial cells, resulting in antisecretory effects in the colon that may alleviate diarrhea and related symptoms (12). Crofelemer has been shown to improve traveler's diarrhea and HIV-associated diarrhea (13,14). It's applicability to symptoms of functional diarrhea is still unclear.

In a Phase II randomized trial, Mangel & Chaturvedi observed the effects of crofelemer in the setting of IBS-D (15). While they did not meet the primary endpoint of altering stool consistency in IBS-D patients, they did find upon further analysis that crofelemer significantly reduced the number of pain- and discomfort-free days in female patients with IBS-D. This study warrants further investigation of the effects of crofelemer in treating symptoms of functional diarrhea.

### B3. DESCRIPTION OF RESEARCH PROTOCOL

#### A. Study Design – Overview, Methods, Procedures

This is a randomized, double-blind, placebo-controlled, parallel group, study is designed to evaluate the efficacy and safety of orally administered crofelemer in patients with diarrhea. The study will consist of a 2-week screening phase, a 4-week double-blind treatment phase, followed by a 4 week open-label extension for both groups.

#### Visit 1

- Informed Consent
- Baseline demographics, medical and treatment history
- Baseline questionnaires via RedCap
- Vitals (height, weight, blood pressure, temperature, heart rate)
- Blood draw for bile acid malabsorption (BAM); mast cell activation, i.e C4, tryptase, histamine; and storing of blood for future studies. BAM is a send-out lab performed by Prometheus Labs. Mast cell activation will be done at a research laboratory at BIDMC.
- Subjects meeting the inclusion and exclusion criteria will enter a screening period of up to 2 weeks during which time subjects will complete daily diary assessment of their bowel symptoms including bowel frequency and use of loperamide via RedCap.
- At the conclusion of the screening period, subjects will be evaluated to determine if they met study entry criteria related to diary compliance, loperamide rescue medication use, and stool consistency (i.e., Bristol Stool Score).

#### Visit 2 (Day 0)

- Adverse event assessment
- Vitals (weight, blood pressure, temperature, heart rate)
- Subjects who meet all conditions for study entry will be randomized into the 4-week double-blind treatment phase. Subjects will be randomized (1:1) to receive crofelemer 125 mg BID or placebo BID for 4 weeks. Approximately 80 patients will be randomly assigned (in a 1:1 ratio) to 125mg crofelemer bid vs. placebo.
- Subjects will continue to complete daily diary assessments of their bowel symptoms and use of loperamide during the 4-week treatment period via RedCap.

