### **C. Subject Selection**

#### Inclusion Criteria

1. Patient is a man or woman aged 18 to 65 years, inclusive, at Screening.
2. Patient has functional diarrhea defined by the Rome IV criteria as loose (mushy) or watery stools  $\geq 25\%$  and hard or lumpy stools  $< 25\%$  of bowel movements
3. Patient has had a colonoscopy performed:
  - a. Within 10 years prior to Prescreening if patient is at least 50 years of age (alternatively, a flexible sigmoidoscopy, double contrast barium enema, or CT colonography within the past 5

- years is acceptable [see recommendations of the American Cancer Society])
- b. Since the onset (if applicable) of any of the following alarm features for patients of any age (see Spiller and Thompson, 2010 – i.e. Patient has documented weight loss within the past 6 months; Patient has nocturnal symptoms; Patient has a familial history of colon cancer; or patient has blood mixed with their stool (excluding any blood from hemorrhoids).
  4. Patient has an average daily stool consistency score (BSS) of  $\geq 5.0$  on days without the use of an anti-diarrheal and at least 3 days with a BSS score  $\geq 5$  on a 1 to 7 scale over the week prior to randomization.
  5. Patient has completed the daily diary on at least 6 of the 7 days during the week prior to randomization AND at least 11 of the 14 days during the 2 weeks prior to randomization.
  6. Patient has not used loperamide rescue medication more than 4 days during the screening period.
  7. Patient is not planning to change his/her usual diet and lifestyle during the course of the study.
  8. Patient is willing to be compliant with study procedures including completing the daily diary during the screening period and throughout the study.
  9. Patient must sign an informed consent document before the initiation of any study-related procedures indicating that he or she understands the purpose of and procedures required for the study and is willing to participate in the study.

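### C4 is drawn before randomisation and defines the only secondary objective, but neither the allocation nor the analysis as described makes use of it

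*Combined protocol and SAP*

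**What the plan says.** - **Objective (B1).** The single secondary objective is whether crofelemer "is more effective in subjects without evidence of bile acid malabsorption (i.e., elevated C4 level". The protocol thus treats C4 as a possible modifier of the drug's effect.
- **Timing of the sample (B3.A, Visit 1).** The visit includes "Blood draw for bile acid malabsorption (BAM); mast cell activation, i.e C4, tryptase, histamine". Eligible patients then "will enter a screening period of up to 2 weeks". Inclusion criterion 5 requires diary entries on "at least 11 of the 14 days during the 2 weeks prior to randomization", so in practice the gap is close to two weeks.
- **Laboratory (B3.A, Visit 1).** "BAM is a send-out lab performed by Prometheus Labs", while the mast-cell tests go to an in-house research laboratory. C4 is listed with the mast-cell markers there and again at Visit 3, although B1 ties it to bile acid malabsorption.
- **Allocation (Visit 2, Day 0).** "Subjects will be randomized (1:1) to receive crofelemer 125 mg BID or placebo BID for 4 weeks"; and "Approximately 80 patients will be randomly assigned (in a 1:1 ratio"). No stratum, block or minimisation is named anywhere.
- **Analysis (B3.B, Data Analysis).** Generic paired tests and comparisons of proportions, with no C4 subgroup, interaction term or adjustment.
- **Not given.** A C4 cut-off, the expected share with elevated C4, and whether the result is available by Day 0.

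**The concern.** If the sponsor's hypothesis is right, response on crofelemer depends on C4 status. When allocation takes no account of C4, the number of elevated-C4 patients in each arm is random. Two things are then at stake in the one trial that will be run. First, the elevated-C4 group may leave very few patients in one arm, which widens the crofelemer-versus-placebo estimate in that group and the contrast between C4 groups. Second, the overall response on crofelemer moves up or down with the number of elevated-C4 patients that arm happens to draw. The sample is already taken before randomisation, so both could be reduced cheaply, and a thin cell cannot be refilled once patients are randomised.

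**Working it through.** **Inputs from the documents.** 80 patients randomised 1:1, so 40 per arm; placebo response 40%; stated power 85%.

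**Assumptions.** The number with elevated C4, m, is varied from 8 to 32 (10-40% of 80). Two-sided alpha is 0.05. For illustration, response is 40% in every cell except crofelemer with normal C4, where it is 72%.

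**The plan's own figure.** The sample size cannot be reproduced, because the crofelemer response, alpha and sidedness are missing. With 40 per arm, 40% on placebo and two-sided alpha 0.05 without continuity correction, 85% power needs about 72.6% on crofelemer. The 72% above is close to that figure.

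**Step 1: chance of a lopsided split.** With 40 of 80 on crofelemer, the number x of elevated-C4 patients in that arm is hypergeometric: P(x) = C(m, x) · C(80−m, 40−x) / C(80, 40). If each patient is allocated by coin toss, x is binomial(m, 0.5).

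**Step 2: precision.** The variance of the C4-by-treatment contrast is proportional to V(x) = 1/x + 1/(m−x) + 1/(40−x) + 1/(40−m+x), compared with 4/m + 4/(80−m) at an even split. For m = 20:
- 10:10: 4/20 + 4/60 = 0.267
- 14:6: 1/14 + 1/6 + 1/26 + 1/34 = 0.306, ratio 1.15
- 15:5: 1/15 + 1/5 + 1/25 + 1/35 = 0.335, ratio 1.26

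**Step 3: interaction power.** Wald test on the risk-difference scale, with the interaction equal to 0.72 − 0.40 = 0.32. For m = 20 at 10:10, SE = √(0.24/10 + 0.24/10 + 0.72·0.28/30 + 0.24/30) = 0.250. Then 0.32/0.250 = 1.28 and power is 0.248.

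Averages are over the hypergeometric splits that leave at least one elevated-C4 patient in each arm.

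| Elevated C4 | 2:1 or worse (coin toss) | 3:1 or worse | Mean rise in contrast variance | Power, unstratified average → even split |
|---|---|---|---|---|
| 8 (10%) | 26% (29%) | 26% | 15% | 0.133 → 0.142 |
| 12 (15%) | 35% (39%) | 11% | 8% | 0.174 → 0.183 |
| 16 (20%) | 16% (21%) | 5% | 5% | 0.211 → 0.218 |
| 20 (25%) | 7% (12%) | 2% | 3% | 0.242 → 0.248 |
| 24 (30%) | 9% (15%) | 0.7% | 2% | 0.268 → 0.273 |
| 32 (40%) | 1% (5%) | 0.1% | 2% | 0.303 → 0.307 |

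The column of 2:1 splits is not smooth because counts are whole numbers. The gain in power is an upper bound: permuted blocks of 4 (an assumed size) can still leave a difference of 2 in the stratum. A bad draw costs more than the average: with 20 elevated patients split 15 on crofelemer and 5 on placebo, power is 0.207.

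**Step 4: the overall comparison.** With 10 elevated patients among 40 on crofelemer, expected response is (30·0.72 + 10·0.40)/40 = 64.0%. With 14 it is (26·0.72 + 14·0.40)/40 = 60.8%. Placebo stays at 40%, so the difference falls by 3.2 points. Its standard error is √(0.64·0.36/40 + 0.40·0.60/40) = 10.8 points, so the shift is about 0.3 standard errors.

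**The case against.** The strongest reply is that the subgroup's size, not its split, makes the C4 comparison weak. With 20 elevated-C4 patients and 40% response in both arms, the 95% half-width for crofelemer minus placebo is 1.96·√(0.24·(1/10 + 1/10)) = 43 points at 10:10, and 1.96·√(0.24·(1/14 + 1/6)) = 47 points at 14:6. Neither is informative, and interaction power is only about 14-31% over 10-40% elevated even with an even split. Unstratified 1:1 allocation is also a legitimate choice at this size, and adjusting for C4 in the analysis would deal with much of the chance imbalance. All of this stands, and it limits the point to a cheap improvement. It does not remove it: adjustment cannot add patients to a thin cell, and the analysis as written makes no adjustment.

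Stratification is also not ready to use. There is no cut-off, the laboratory and turnaround for C4 are unclear, and a pending list does not balance C4 among the patients on it. This stands too and shapes the fix.

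A reader might infer several stronger things that the documents do not support:
- **That the elevated-C4 group is small.** No share is given, and at 40% a 2:1 split is rare.
- **That the C4 result is known at randomisation.** Only the draw is placed before it.
- **That the plan chose to disregard C4.** It is silent on the randomisation method altogether.
- **That the primary comparison is biased.** Imbalance under randomisation is chance error, already covered by the test's error rate. The stated hypothesis concerns response to crofelemer, so the shift comes mainly through that arm.

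**Conclusion.** The point holds as a low-cost improvement, not as an error in the plan. A variable drawn before randomisation, on which the only secondary objective depends, appears in neither the allocation nor the analysis as described. If 10-25% of 80 patients have elevated C4, that group splits 2:1 or worse in about 7-35% of trials with fixed arms of 40. The average price is a contrast variance about 3-15% higher and about one point of interaction power or less. The split probabilities rest on the assumed share and on 40 per arm; the power figures rest also on the assumed 72% versus 40% response. Stratifying would guard against a bad draw in this one trial. It would not make the C4 comparison adequately powered.

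**What to change.** 1. State the C4 cut-off for elevated, and say which laboratory measures C4 and whether its result is expected before Day 0. Reconcile the Visit 1 and Visit 3 wording, which groups C4 with the mast-cell markers, with B1.
2. Describe the randomisation method. Use 1:1 permuted blocks stratified by Visit 1 C4 (elevated versus not) for patients whose result is back by Day 0, and a separate pending list for the rest, so that no visit is delayed.
3. Include baseline (Visit 1) C4 status in the between-arm analysis for all patients, whenever the result is reported. Patients on the pending list depend on this step. Prespecify the C4-by-arm comparison and label it exploratory.

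The cost is a list with two or three strata and a few sentences of text, with no new test, visit or patient. The downsides are slightly more list management, some incomplete blocks, dependence on laboratory turnaround, and no C4 balance among patients on the pending list. If most results come back late, most of the benefit of stratifying is lost and step 3 carries the point.

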#### Visit 3 (Week 4)

- Adverse event assessment

- Vitals (weight, blood pressure, temperature, heart rate)
- Blood draw for mast cell activation, i.e C4, tryptase, histamine; and storing of blood for future studies
- Subjects will return their unused study drug to the study team for IP accountability.
- Subjects completing the 4 week double-blind treatment phase will be eligible to enter an open-label extension for 4 weeks during which all subjects will receive crofelemer 125 mg BID.
- Subjects will continue to complete daily diary assessments of their bowel symptoms and use of loperamide during the 4-week treatment period via RedCap.

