#### **Visit 4 (Week 8)**

- Adverse event assessment
- Vitals (weight, blood pressure, temperature, heart rate)
- Subjects will return their unused study drug to the study team for IP accountability

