#### Blood Collection

Any blood that is remaining after the analysis is completed will be stored frozen indefinitely at BIMDC for use in future studies. The sample will remain de-identified, but be labeled with the unique subject code. Information related to the subject's diagnosis, treatment, and study results will be retained and possibly used in future analysis and more information becomes identified regarding functional bowel disorders. PHI related to the stored samples will not be used in the future analysis and will be kept on BIDMC's secure server. Any samples that may be shared with collaborators will contain the subject code, but will not have any identifiable information or PHI.

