**B5. POSSIBLE RISKS AND ANALYSIS OF RISK/BENEFIT RATIO****Safety**

Possible risks of crofelemer include upper respiratory tract infection, bronchitis, cough, flatulence, increased bilirubin, nausea, back pain, arthralgia, UTI, nasopharyngitis, musculoskeletal pain, hemorrhoids, giardiasis, anxiety, increased alanine aminotransferase, abdominal distention.

There is a possible risk of loss of confidentiality, however every effort will be made to ensure patient confidentiality which includes but is not limited to only discussing medical information in a private clinical setting and collecting information necessary to accomplish the research purpose. Physical data will be kept in a locked room that only the research team have access to. Electronic data will be kept on the secure server with access granted only to the individuals on the research staff.

The risk/benefit ratio of the study is favorable for the patient due to the limited options for treating functional diarrhea.

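### Raised ALT and raised bilirubin are listed as possible crofelemer risks, but no visit measures either, so as planned the trial does not assess symptomless rises.

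*Combined protocol and SAP*

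**What the plan says.** Section B1 gives two primary objectives, and one of them is "To evaluate the overall safety and tolerability of crofelemer in the treatment of diarrhea".

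Section B5 (Safety) lists possible risks of the drug. Two entries are laboratory findings and not symptoms; they appear in the runs "cough, flatulence, increased bilirubin, nausea" and "increased alanine aminotransferase, abdominal distention". The list gives no rate, severity or statement of cause for any entry.

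Section B3.A sets out four visits, two of them with blood draws:

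- Visit 1: "Blood draw for bile acid malabsorption (BAM); mast cell activation, i.e C4, tryptase, histamine; and storing of blood for future studies".
- Visit 3 (Week 4): "Blood draw for mast cell activation, i.e C4, tryptase, histamine; and storing of blood for future studies".

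Visits 2 and 4 have adverse event assessment and vital signs but no blood draw. On leftover blood, the Blood Collection paragraph says "Any blood that is remaining after the analysis is completed will be stored frozen indefinitely", for use in future studies. On numbers, Visit 2 says "Approximately 80 patients will be randomly assigned (in a 1:1 ratio) to 125mg crofelemer bid vs. placebo". The Data Analysis paragraph in B3.B plans no laboratory safety analysis.

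**The concern.** The protocol names two risks that only a blood test can establish, makes safety a primary objective, and draws blood at both ends of the blinded phase, yet runs neither test. Adverse event assessment and vital signs serve the symptomatic part of the safety objective. For the liver they would pick up only symptomatic illness or a result that happened to come from outside care.

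Timing adds to this. The 4-week blinded phase is the only part of the study with a placebo comparison; in the extension everyone takes crofelemer. Liver tests by randomised arm can be described only from that phase. As the plan stands, the final report could say nothing systematic about two risks on the protocol's own list, and the investigator would have no scheduled liver result to look at as patients move into the extension.

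**Working it through.** The plan gives no figure on this point to reproduce. The check sets the visit schedule against the risk list, then asks what the tests would show if they were added.

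**1. Schedule against risk list**

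| Visit | Blood drawn | ALT or bilirubin |
|---|---|---|
| 1 (screening) | bile acid and mast cell markers, storage | no |
| 2 (Day 0) | none listed | no |
| 3 (Week 4) | C4, tryptase, histamine, storage | no |
| 4 (Week 8) | none listed | no |

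B5 lists 16 risks, and 2 of them are laboratory findings. Scheduled measurements of either: 0 across 4 visits. Exclusion criterion 6 rules out an unstable hepatic condition, but it names no test or threshold and applies only at entry.

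**2. Inputs for what testing would show**

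About 80 patients randomised 1:1 gives 80/2 = 40 per arm (Visit 2). The protocol states no dropout rate. Assuming 20% attrition by Week 4, 0.8 × 40 = 32 per arm. The event rates below are also assumptions, because the documents give none.

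**3. Mean change, crofelemer against placebo**

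For a two-sample t-test with two-sided alpha 0.05 and 80% power, the detectable difference is approximately (1.960 + 0.842) × √(2/n) SD. With n = 40 this is 2.802 × 0.2236 = 0.627. The exact t calculation gives 0.634 SD with 40 per arm and 0.711 SD with 32. The documents give no SD for ALT or bilirubin, so these cannot be turned into laboratory units.

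**4. Raised values within the crofelemer arm**

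If no raised value is seen in n patients, the one-sided 95% upper bound on the rate is 1 − 0.05^(1/n):

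- n = 40: 7.2%
- n = 32: 8.9%

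The chance of seeing at least one is 1 − (1 − p)^n:

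| Assumed rate p | n = 40 | n = 32 |
|---|---|---|
| 2% | 55% | 48% |
| 5% | 87% | 81% |
| 10% | 98.5% | 97% |

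These figures concern raised values from any cause. If 5% of patients had raised values regardless of drug, none would be seen among 40 with probability 0.95^40 = 13%; at 10% it is 0.90^40 = 1.5%. A single raised value on crofelemer is therefore weak evidence about the drug unless the Visit 1 value is known and taken into account.

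**5. Comparing counts between arms**

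With 40 per arm, Fisher's exact test (two-sided) gives p = 0.055 for 5 against 0 and p = 0.026 for 6 against 0, so 6 against 0 is the smallest such split below 0.05. Power is the sum of the binomial probabilities of all pairs of counts with p < 0.05:

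| Assumed rates | Exact Fisher power, 40 per arm |
|---|---|
| 10% v 2% | about 11% |
| 10% v 5% | about 4% |
| 15% v 5% | about 18% |

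By the normal approximation, 80% power needs about 22% on crofelemer against 2% on placebo.

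**The case against.** The strongest defence is that no stated requirement is broken. B1 promises overall safety and tolerability, not laboratory safety, and adverse event assessment and vital signs at Visits 2 to 4 serve that promise. The B5 list is undifferentiated: it sits liver tests beside bronchitis, giardiasis and anxiety, and it commits the study to no monitoring. This stands. The point is an improvement the protocol's own list suggests, not a breach.

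Three stronger readings are tempting, and the documents do not support them.

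- *The trial cannot detect or compare rises.* Blood from Visits 1 and 3 is stored under the subject code, and treatment and results are retained, so a later assay by arm is not ruled out. The accurate statement is that no such assay is planned. Whether the samples would suit one is not stated, a later result could not inform care during the trial, and Week 8 has no sample at all.
- *Patients are exposed to a known liver hazard.* The documents give no rate or severity, and nothing in them shows that rises are likely over 4 or 8 weeks.
- *Testing would settle whether rises are more common on crofelemer.* With 40 per arm it would not, as the Fisher powers show. Counts would be descriptive.

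Two practical objections also stand. A count of everyone above the upper limit would mix new rises with values already raised at entry. And the laboratories named at Visit 1 (a send-out laboratory for bile acid testing and a research laboratory for mast cell markers) are not described as doing clinical chemistry, so the cost is more than the reagents. Both are met in the change proposed.

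**Conclusion.** The omission is real and rests on the visit lists alone: two of the 16 named risks are laboratory findings, and neither is measured at any of the four visits. As planned, symptomless rises in ALT or bilirubin go unassessed under a primary safety objective.

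This is a cheap improvement, not a flaw that threatens the trial; the efficacy comparison is untouched. What the tests would add is a description of liver values by arm at Week 4 and the ability to detect a mean shift of about 0.63 SD (0.71 SD under the assumed attrition). They would not support a reliable comparison of how often values rise. The power figures rest on 40 or 32 tested per arm and on assumed event rates. The finding itself depends on neither.

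**What to change.** 1. Add ALT and total bilirubin to the blood draws already made at Visit 1 and Visit 3 (B3.A).
2. Make both results available to the investigator for clinical review. No fixed threshold or hold on open-label drug is proposed; action is a matter of clinical judgement.
3. Add to Data Analysis (B3.B), by randomised arm: (a) the between-arm difference in change from Visit 1 to Week 4, with a 95% confidence interval; (b) descriptively, the number of patients with a new or worsened value above the laboratory's upper limit of normal, shown separately from those already raised at Visit 1. Item (a) has to be written out, because the paired pre-post tests now specified for continuous data do not compare arms.
4. State in the safety conclusion that liver tests were not assessed during the open-label extension. If that is unacceptable, a Week 8 draw would add one venepuncture per patient and up to 80 samples.

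Cost: a short amendment and up to 120 + 80 = 200 samples, with two routine assays on each. The 120 arises because the sample size paragraph recruits 120 to enrol 80, so up to 40 of those tested at Visit 1 would never be randomised. With the assumed 20% attrition the total is 120 + 64 = 184. No new venepuncture is needed at Visits 1 and 3, but an extra tube and a clinical laboratory route may be, and incidental rises will need follow-up. Eligibility, dosing and sample size do not change.
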